**Table 1. Diagnosis codes for inclusion criteria.**

KCD-6 	KCD-7 
I48 (Atrial fibrillation and flutter)	I48 (Atrial fibrillation and flutter)
I480 (Atrial fibrillation)	I480 (Paroxysmal atrial fibrillation)
I481 (Atrial flutter)	I481 (Persistent atrial fibrillation)
	I482 (Chronic atrial fibrillation)
	I483 (Typical atrial flutter)
	I484 (Atypical atrial flutter)
	I489 (Atrial fibrillation and atrial flutter, unspecified)

KCD-6, Korean version of ICD-10 (6th revision); KCD-7, Korean version of ICD-10 (7th revision)

1) KCD-6 diagnosis codes will be used from 1 July 2015 to 31 December 2015.

2) KCD-7 diagnosis codes will be used from 1 January 2016 to 30 November 2016.

[NOTE] KCD code is based on ICD-10 and almost similar, but KCD code is slightly different from ICD-10 (e.g., ICD-10 is more subdivided and extensive than KCD code).

3. Patients prescribed aspirin, warfarin, or NOACs during intake period (from July 1, 2015 to November 30, 2016)

*[Note] NOACs include apixaban, dabigatran, and rivaroxaban.*

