Individual outcome of primary outcome	Secondary effectiveness outcome	HIRA database	
Claims with the following KCD codes in all diagnosis codes (main and sub-diagnosis codes) whichever came first (i.e., the first occurred event will be used):
 
 
1. Ischemic stroke: G459, I63, I693
 
2. Systemic embolism: I74
 
3. Hemorrhagic stroke: I60, I61, I62, I690, I691, I692
 
 
[NOTE] Hospitalization and CT or MRI codes (brain CT or MRI for ischemic stroke and hemorrhagic stroke; any CT or MRI for systemic embolism) were also required for identification. For CT or MRI codes, please see above.

Major bleeding	Primary safety outcome	HIRA database	
Bleeding requiring hospitalization will be identified using hospital claims which had a bleeding diagnosis code as the first occurred KCD code and it will be consisted of intracranial hemorrhage (ICH) and gastrointestinal (GI) bleeding, and other bleeding. All KCD diagnosis codes (main and sub-diagnosis codes) will be used. Especially, hospitalization and brain CT or MRI codes will be needed to identify ICH.
 
 
- Intracranial (I60, I61, I62, I690, I691, I692, S064, S065, S066, S068)
 
- Gastrointestinal bleeding (I850, I983, K2211, K226, K228, K250, K252, K254, K256, K260, K262, K264, K266, K270, K272, K274, K276, K280, K282, K284, K286, K290, K3181, K5521, K625, K920, K921, K922)
 
- Other bleeding (D62, H448, H3572, H356, H313, H210, H113, H052, H470, H431, I312, N020-N029, N421, N831, N857, N920, N923, N930, N938, N939, M250, R233, R040, R041, R042, R048, R049, T792, T810, N950, R310, R311, R318, R58, T455, Y442, D683)
 

Individual outcome of major bleeding	Secondary safety outcome	HIRA database	
Individual outcome of ICH (diagnosis codes in all main and sub-diagnosis codes + hospitalization + brain CT or MRI), gastrointestinal bleeding (diagnosis codes in all main and sub-diagnosis codes + hospitalization), and other bleeding (diagnosis codes in all main and sub-diagnosis codes + hospitalization).
 
For codes, please see above.

Variable	Role	Data source(s)	Operational definition
Types of health insurance	Covariates	HIRA database	Types of health insurance divided as the following: 1. National Health Insurance 2. Medical aid

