6. For the comparison of “NOAC versus NOAC”, and “NOAC versus warfarin”, patients with any OACs (apixaban, dabigatran, rivaroxaban, or warfarin) in the pre-index period (from 1 year prior to the day before index date)
 - *[NOTE] Patients prescribed antiplatelets in the pre-index period will not be excluded.*
7. For the comparison of “NOAC versus aspirin”, patients with following medications in the pre-index period (from 1 year prior to the day before index date)
 - NOAC user: OACs (apixaban, dabigatran, rivaroxaban, warfarin)
 - Aspirin user: none
 - *[NOTE] NOAC user is defined as OAC naïve user and aspirin user is allowed to have OACs or antiplatelets in the pre-index period.*

Cohorts

To avoid increasing type I error when multiple comparisons occur, this full analysis set will be splitted into multiple sub-analysis sets as follows:

1. NOAC vs NOAC (both as OAC naïve users)
 - A. Sub-dataset 1: patients with index treatment of apixaban and patients with index treatment of dabigatran
 - B. Sub-dataset 2: patients with index treatment of apixaban and patients with index treatment of rivaroxaban
 - C. Sub-dataset 3: patients with index treatment of dabigatran and patients with index treatment of rivaroxaban

[NOTE] The index date will be defined as date of the first prescription of NOAC in patients with NVAF. To identify new users, a look-back observation period from 1 year prior to the day before the index date will be used and must indicate no OAC use during this period. The diagnosis date of NVAF could occur from January 1, 2007 up to and including the index date.

2. NOAC vs warfarin (both as OAC naïve users)
 - A. Sub-dataset 4: patients with index treatment of apixaban and patients with index treatment of warfarin
 - B. Sub-dataset 5: patients with index treatment of dabigatran and patients with index treatment of warfarin
 - C. Sub-dataset 6: patients with index treatment of rivaroxaban and patients with index treatment of warfarin

[NOTE] The index date will be defined as date of the first prescription of NOAC or warfarin in patients with NVAF. To identify new users, a look-back observation period from 1 year prior to the day before the index date will be used and must indicate no OAC use during this period. The diagnosis date of NVAF could occur from January 1, 2007 up to and including the index date.

3. NOAC (OAC naïve user) vs aspirin (no restrictions of antiplatelet or OAC use in the pre-index period)

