 - A. Sub-dataset 7: patients with index treatment of apixaban and patients with index treatment of aspirin
 - B. Sub-dataset 8: patients with index treatment of dabigatran and patients with index treatment of aspirin
 - C. Sub-dataset 9: patients with index treatment of rivaroxaban and patients with index treatment of aspirin

[NOTE] The index date will be defined as date of the first prescription of NOAC or aspirin in patients with NVAF during the intake period (from July 1, 2015 to November 30, 2016). To identify NOAC users, a look-back observation period from 1 year prior to the day before the index date will be used and must indicate no OAC use during this period. However, OAC use or antiplatelet use during a look-back observation period from 1 year prior to the day before the index date will be allowed for aspirin users. The diagnosis date of NVAF could occur from January 1, 2007 up to and including the index date.

Each patient was followed until discontinuation or switching of index treatment, outcome occurrence, or study ends (November 30, 2016).

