4.2 SAFETY ENDPOINTS

Table 2. Safety Endpoints

Variable	Role	Operational definition
Major bleeding	Primary safety outcome	Bleeding requiring hospitalization will be identified using hospital claims which had a bleeding diagnosis code as the first occurred KCD code and it will be consisted of intracranial hemorrhage (ICH) and gastrointestinal (GI) bleeding, and other bleeding (Appendix 2, Table 8). All KCD diagnosis codes (main and sub-diagnosis codes) will be used. Especially, hospitalization and brain CT or MRI codes will be needed to identify ICH.
Individual outcome of major bleeding	Secondary safety outcome	Individual outcome of ICH (diagnosis codes in all main and sub-diagnosis codes + hospitalization + brain CT or MRI), gastrointestinal bleeding (diagnosis codes in all main and sub-diagnosis codes + hospitalization), and other bleeding (diagnosis codes in all main and sub-diagnosis codes + hospitalization)

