Gastrointestinal bleeding	I850, I983, K2211, K226, K228, K250, K252, K254, K256, K260, K262, K264, K266, K270, K272, K274, K276, K280, K282, K284, K286, K290, K3181, K5521, K625, K920, K921, K922
Other bleeding	D62, H448, H3572, H356, H313, H210, H113, H052, H470, H431, I312, N020-N029, N421, N831, N857, N920, N923, N930, N938, N939, M250, R233, R040, R041, R042, R048, R049, T792, T810, N950, R310, R311, R318, R58, T455, Y442, D683
*Brain CT/MRI	CT: HA441, HA451, HA461, HA471, HA851 MRI: HE101, HE102, HE135, HE201, HE202, HE235, HE301, HE302, HE401, HE402, HE501, HE502, HE535

*Brain CT/MRI will be used to define intracranial hemorrhage.

Table 9. CHA₂DS₂-VASc Score

Condition	KCD code	Point
Congestive heart failure	I50	1
Hypertension	I10-I15	1
Age	75+ years	2
Diabetes	E10-E14	1
Stroke	I63, I693 G459	2
Vascular disease	I21, I252, I70-I73	1
Age	65-74 years	1
Sex	Female	1

Table 10. HAS-BLED Score

Condition	KCD code	Point
Hypertension	I10-I15	1
Abnormal renal function	N183, N184	1
Abnormal liver function	B15-B19, C22, D684, I982, I983, K70-K77, Z944	1
Stroke	I63, I693, G459	1
Bleeding history or Predisposition*	Codes in Table 8	1
Labile INR	Not measurable	Not applicable
Elderly	65+ years	1
Drug therapy	Antiplatelets, NSAIDs	1
Alcoholism	E244, F10, G312, G621, G721, I426, K292, K70, K860, O354, P043, Q860, T510, X45, X65, Y15, Y90-Y91, Z502, Z714, Z721	1

* Blood transfusion will also be used to define other bleeding history (see Table 14 for blood transfusion codes).

Table 11. Charlson Comorbidity Index

Condition	KCD code	Point
Cerebrovascular disease	G45.x, G46.x, H34.0, I60.x-I69.x	1
Congestive heart failure	I09.9, I11.0, I13.0, I13.2, I25.5, I42.0, I42.5-I42.9, I43.x, I50.x, P29.0	1
Chronic pulmonary disease	I27.8, I27.9, J40.x-J47.x, J60.x-J67.x, J68.4, J70.1, J70.3	1
Dementia	F00.x-F03.x, F05.1, G30.x, G31.1	1
Diabetes without chronic complication	E10.0, E10.1, E10.6, E10.8, E10.9, E11.0, E11.1, E11.6, E11.8, E11.9, E12.0, E12.1, E12.6, E12.8, E12.9, E13.0, E13.1, E13.6, E13.8, E13.9, E14.0, E14.1, E14.6, E14.8, E14.9	1
Mild liver disease	B18.x, K70.0-K70.3, K70.9, K71.3-K71.5, K71.7, K73.x, K74.x, K76.0, K76.2-K76.4, K76.8, K76.9, Z94.4	1
Myocardial infection	I21.x, I22.x, I25.2	1
Peripheral vascular disease	I70.x, I71.x, I73.1, I73.8, I73.9, I77.1, I79.0, I79.2, K55.1, K55.8, K55.9, Z95.8, Z95.9	1
Peptic ulcer disease	K25.x-K28.x,	1
Rheumatologic disease	M05.x, M06.x, M32.x-M34.x M31.5M35.1, M35.3, M36.0	1

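### T455 and Y442, which on ICD-10 meanings record an anticoagulant's adverse effect and not a bleed, count alone as major bleeding, so ascertainment differs by drug in the NOAC-versus-aspirin comparisons

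*Protocol*

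**What the plan says.** Protocol 8.3 builds major bleeding from intracranial, gastrointestinal and other bleeding: "Bleeding requiring hospitalization will be identified using hospital claims which had a bleeding diagnosis code as the first occurred KCD code". The other-bleeding list ends "N950, R310, R311, R318, R58, T455, Y442, D683". SAP Appendix 2, Table 8 ends its list the same way ("R048, R049, T792, T810, N950, R310, R311, R318, R58, T455, Y442, D683"), so this is not a slip in one document.

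SAP 4.2 sets the conditions. On diagnosis position: "All KCD diagnosis codes (main and sub-diagnosis codes) will be used". For the third component alone it asks for "other bleeding (diagnosis codes in all main and sub-diagnosis codes + hospitalization". Only intracranial haemorrhage also needs brain CT or MRI. Transfusion codes (SAP Table 14) serve baseline bleeding history, not the outcome.

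Neither document labels T455, Y442 or D683. The note under Protocol Table 1 says "KCD code is based on ICD-10 and almost similar, but KCD code is slightly different from ICD-10".

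SAP 3.1 defines nine pairwise sub-datasets. Numbers 1 to 6 have an anticoagulant in both arms, for example "patients with index treatment of apixaban and patients with index treatment of warfarin". Numbers 7 to 9 set a NOAC against aspirin, for example "patients with index treatment of apixaban and patients with index treatment of aspirin". The only sensitivity analysis named (Protocol 8.7, SAP 5.1) is multinomial IPTW. None varies the code list.

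**The concern.** A safety outcome compared between drugs should be equally detectable in every arm. On the ICD-10 meanings, T455 and Y442 record exposure to an anticoagulant together with an excess dose or an adverse effect. They do not in themselves record bleeding, and the list has no matching code for aspirin or other antiplatelets.

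Two things are at stake:

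- In sub-datasets 7 to 9, part of the outcome is in practice open to the NOAC arm only. Matching, weighting and covariate adjustment balance baseline characteristics; they cannot repair an outcome whose detection depends on the exposure.
- In all sub-datasets, an admission without a bleed can count as a major bleed. Follow-up ends at the outcome (Protocol 8.3, Follow-up period), so a counted non-bleed also hides a true bleed that comes later.

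**Working it through.** The plan gives no bleeding rate, event count, hazard ratio or power for this outcome, so there is no figure of its own to reproduce. The study size of about 150,000 is a head count from disease statistics. What follows is an illustration under stated assumptions.

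**Inputs.** Let s be the share of an arm's counted events that rest only on the codes at issue, with no other qualifying code. The documents give no value. I take s = 1%, 5% and 10% for the NOAC arm and about 0 for aspirin. Significance is p < 0.05 (Protocol 8.7), taken as two-sided, with 1:1 matching (SAP 5.1).

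**Formula.** If events that qualify in another way occur at rate R, the counted rate is R/(1 − s). Hence observed HR = true HR × (1 − s_ref)/(1 − s_NOAC).

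**NOAC versus aspirin, true HR 1.00, aspirin share 0.** The chance of p < 0.05 is Φ(z − 1.96) + Φ(−z − 1.96), with z = √(D/4) × |ln HR| and D total events (both values of D are assumed).

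| s_NOAC | Observed HR | Chance of p < 0.05, D = 200 | D = 1,000 |
|---|---|---|---|
| 1% | 1/0.99 = 1.01 | 5.1% | 5.3% |
| 5% | 1/0.95 = 1.05 | 6.5% | 12.8% |
| 10% | 1/0.90 = 1.11 | 11.6% | 38.4% |

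A true HR of 0.80 would appear as 0.80/0.99 = 0.81, 0.80/0.95 = 0.84 or 0.80/0.90 = 0.89. If the aspirin share were 1% instead of 0, the 5% row would give 0.99/0.95 = 1.04.

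**NOAC versus NOAC or warfarin.** Equal shares cancel: 0.95/0.95 = 0.90/0.90 = 1.00. Only unequal shares move the ratio. With 3% in the NOAC arm and 10% in the warfarin arm it is 0.90/0.97 = 0.93; reversed, it is 0.97/0.90 = 1.08. Nothing in the documents shows which pattern applies, if either.

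**Other uses of Table 8.** The same codes define HAS-BLED bleeding history (SAP Table 10), which is a candidate propensity covariate (SAP 5.1). They also define baseline bleeding (footnote to SAP Table 5) and the events preceding a switch or discontinuation (SAP Table 3). In sub-datasets 7 to 9 only aspirin users may have had an OAC in the year before index, so the baseline covariate may also depend on drug exposure, there in the aspirin arm.

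**The case against.** - **The meanings are not in the documents.** This is true, and the note under Protocol Table 1 says KCD differs slightly from ICD-10. The point depends on a label check that the sponsor can make. That lowers confidence but does not remove the issue.
- **The effect may be trivial.** T455 and Y442 are 2 of 84 listed codes (counting N020 to N029 as ten). If nearly all such claims also carry a bleeding code, s is close to zero. That stands: at 1% the distortion is 0.01 on the hazard ratio.
- **It is partly contained.** Intracranial and gastrointestinal bleeding are separate secondary outcomes and do not use these codes. Protocol 8.9.1 also acknowledges coding error. Both are true, but the primary safety outcome is still the composite, and a general caveat does not cover a code that is open to one arm.
- **The aspirin arm is not sealed off.** A reader might infer that these events are impossible there. The documents do not support that. Aspirin users may have prior OAC use. SAP Table 3 also counts a switch only after discontinuation, so an OAC added to continuing aspirin would not be a switch on that wording (Protocol 8.3 is broader). The aspirin share is near zero, not zero by design.
- **D683.** A reader might class it with the other two as an anticoagulant-drug-only code. On its ICD-10 label it names a haemorrhagic disorder due to circulating anticoagulants. That is a bleeding condition, and the label is not confined to drugs. Its weakness is only that aspirin has no counterpart.

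**Conclusion.** The concern holds for T455 and Y442, subject to confirmation of their labels in KCD-6 and KCD-7. In sub-datasets 7 to 9 the outcome definition depends on the drug, and any events resting only on these codes raise the NOAC hazard ratio. That direction runs against the sponsor's product. In all nine comparisons the definition admits admissions without a bleed.

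A reader might go further and infer that the list favours NOACs over warfarin, because over-anticoagulation would be coded more often with warfarin. The documents do not support this: both arms are anticoagulated, equal shares leave a null ratio at 1.00, and no coding frequencies are given.

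The size cannot be derived from the documents. For assumed NOAC-arm shares of 1% to 10% and an aspirin share of about 0, a true hazard ratio of 1.00 appears as 1.01 to 1.11. This should be fixed, with medium confidence; the unknown size does not justify calling it essential.

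**What to change.** 1. Confirm the labels of T455, Y442 and D683 in KCD-6 and KCD-7.
2. Delete T455 and Y442 from the other-bleeding list in Protocol 8.3 and SAP Table 8. A rule that keeps them when a second bleeding code is present is not needed. A gastrointestinal or other-bleeding code on the claim already qualifies by itself, and an intracranial companion code would let such cases in without the required brain imaging.
3. Keep D683 in the main definition and add a sensitivity analysis without it.
4. Report the present list as a further sensitivity analysis, giving per arm the number of events that rest on these codes alone. This shows the actual shares. It also keeps a result on the present definition, which matters because the amendment history says the endpoint was changed to match a harmonized protocol (whether the code list is shared is not stated).
5. Carry the change into HAS-BLED bleeding history, baseline bleeding and the preceding-event definitions, which use the same table.

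The cost is slightly fewer counted events, one extra programme run, and a protocol amendment, which Protocol 8.7 foresees for major changes to primary endpoint definitions.

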## 1. LIST OF ABBREVIATIONS

Abbreviation	Definition
AIDS	Acquired immune deficiency syndrome
CABG	Coronary Artery Bypass Graft surgery
CHA 2 DS 2 -VASc	Clinical stroke risk prediction tool based on comorbidities of congestive heart failure, hypertension, elderly age, diabetes mellitus, prior stroke or thromboembolism, vascular disease, and gender.
HAS-BLED	Clinical major bleeding risk score based on comorbidities of hypertension, abnormal renal and liver function, prior stroke, bleeding history, labile international normalized ratio values of anticoagulation level, elderly age, and concomitant drug or alcohol use.
HIRA	Health Insurance Review & Assessment Service
HIV	Human immunodeficiency virus
ICD-10	International Classification of Diseases 10 th revision
ICJME	International Committee of Medical Journal Editors
KCD-6	Korean Standard Classification of Diseases 6 th revision
KCD-7	Korean Standard Classification of Diseases 7 th revision
MI	Myocardial infarction
MPR	Medication possession ratio
NOAC	Non vitamin K antagonist oral anticoagulants
NSAIDs	Nonsteroidal anti-inflammatory drugs
NVAF	Nonvalvular atrial fibrillation
OAC	Oral anticoagulants
PCI	Percutaneous coronary intervention

Abbreviation	Definition
PPI	Proton pump inhibitor
TE	Thromboembolism
TIA	Transient ischemic attack

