### 8.2.2 Exclusion criteria

Patients meeting any of the following criteria will not be included in the study.

1. Medical claims indicating diagnosis or procedure for hip/knee replacement surgery within 6 weeks prior to index date
2. Medical claims indicating a diagnosis code indicative of rheumatic mitral valvular heart disease, mitral valve stenosis during the 12-month baseline period  
(Valvular AF / Prosthetic heart valves)
3. Medical claims indicating a diagnosis code of VTE (Venous thromboembolism) during the 12-month baseline period
4. Medical claims indicating a diagnosis or procedure code of transient AF, or cardiac surgery during the 12-month baseline period

(Thyrotoxicosis, Hypertrophic cardiomyopathy, Elective defibrillation, radiofrequency ablation, or left atrial appendage occlusion)

5. Medical claims indicating a diagnosis code of other conditions during the 12-month baseline period  
(End-stage chronic kidney disease / Kidney transplant / Dialysis / Pericarditis)
6. For the comparison of “NOAC versus NOAC”, and “NOAC versus warfarin”, patients with any OACs (apixaban, dabigatran, rivaroxaban, or warfarin) in the pre-index period (from 1 year prior to the day before index date)
  - *[NOTE] Patients prescribed antiplatelets in the pre-index period will not be excluded.*
7. For the comparison of “NOAC versus aspirin”, patients with following medications in the pre-index period (from 1 year prior to the day before index date)
  - NOAC user: OACs (apixaban, dabigatran, rivaroxaban, warfarin)
  - Aspirin user: none
  - *[NOTE] NOAC user is defined as OAC naïve user and aspirin user is allowed to have OACs or antiplatelets in the pre-index period.*

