### 8.3 Variables

Variable	Role	Data source(s)	Operational definition
Composite of hemorrhagic stroke, ischemic stroke and systemic embolism	Primary effectiveness outcome	HIRA database	
Claims with the following KCD codes in all diagnosis codes (main and sub-diagnosis codes) whichever came first (i.e., the first occurred event will be used):
 

1. Ischemic stroke: G459, I63, I693

2. Systemic embolism: I74

3. Hemorrhagic stroke: I60, I61, I62, I690, I691, I692

 
[NOTE] Hospitalization and CT or MRI codes (brain CT or MRI for ischemic stroke and hemorrhagic stroke; any CT or MRI for systemic embolism) were also required for identification.
 
*Brain CT or MRI:
 
CT: HA441, HA451, HA461, HA471, HA851
 
MRI: HE101, HE102, HE135, HE201,

Variable	Role	Data source(s)	Operational definition

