CHA 2 DS 2 -VASC	Covariates	HIRA database	CHA 2 DS 2 -VASC as continuous data or dichotomous data. The score will be calculated using the following KCD codes (refer to SAP-Appendix 2, Table 9): 1. Congestive heart failure 2. Hypertension 3. Diabetes mellitus 4. Stroke/TIA/TE 5. Vascular disease 6. Age $\geq$ 75 7. Age 65-74 8. Sex (female)
HAS-BLED	Covariates	HIRA database	HAS-BLED as continuous data or dichotomous data. The score will be calculated using the following KCD codes (refer to SAP-Appendix 2, Table 10): 1. Hypertension 2. Abnormal renal function 3. Abnormal liver function 4. Stroke 5. Bleeding history or predisposition 6. Age $>$ 65 7. Antiplatelet or NSAID use 8. Alcoholism
Charlson Comorbidity Index	Covariates	HIRA database	Charlson Comorbidity Index as continuous data or dichotomous data. The index will be calculated using the following KCD codes (Refer to SAP-Appendix 2, Table 11): 1. Myocardial infarction 2. Congestive heart failure 3. Peripheral vascular disease 4. Cerebrovascular disease 5. Dementia 6. Chronic pulmonary disease 7. Rheumatic disease 8. Peptic ulcer disease 9. Mild liver disease 10. Diabetes without chronic complication 11. Diabetes with chronic complication 12. Hemiplegia or paraplegia 13. Renal disease 14. Any malignancy, including lymphoma and leukemia, except malignant neoplasm of skin 15. Moderate or severe liver disease 16. Metastatic solid tumor 17. AIDS/HIV

Variable	Role	Data source(s)	Operational definition
Medication use	Covariates	HIRA database	
It will be consisted of the following:
 
 
1. History of NSAIDs
 
2. History of antiplatelet
 
3. History of PPI
 
4. History of H2-receptor antagonists
 
5. History of antiarrhythmics
 
6. History of digoxin
 
7. History of statins
 

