4.4 COVARIATES

Table 4. Baseline Variables

Variable	Role	Operational definition
Age	Baseline characteristic and potential confounder	Age at index date
Sex	Baseline characteristic and potential confounder	
 1. Male 2. Female
Types of health insurance	Baseline characteristic and potential confounder	
Types of health insurance divided as the following:
 
 1. National Health Insurance 2. Medical aid

NIS Protocol <X9001134>
 Statistical Analysis Plan
 <Version 3.0> <03 May 2018>

Variable	Role	Operational definition
CHA ₂ DS ₂ -VASC	Baseline characteristic and potential confounder	
CHA₂DS₂-VASC as continuous data or dichotomous data. The score will be calculated using the following KCD codes (Appendix 2, Table 9):
 
 1. Congestive heart failure 2. Hypertension 3. Diabetes mellitus 4. Stroke/TIA/TE 5. Vascular disease 6. Age ≥ 75 7. Age 65-74 8. Female
HAS-BLED	Baseline characteristic and potential confounder	
HAS-BLED as continuous data or dichotomous data. The score will be calculated using the following KCD codes (Appendix 2, Table 10):
 
 1. Hypertension 2. Abnormal renal function 3. Abnormal liver function 4. Stroke 5. Bleeding history or predisposition: refers to any bleeding codes 6. Age > 65 7. Antiplatelet or NSAID use 8. Alcoholism 
[Note] Labile international normalized ratio is not available in HIRA data and does not apply to patients on aspirin, or NOACs, so the modified HAS-BLED score has a maximum value of 8 instead of 9.

Charlson Comorbidity Index	Baseline characteristic and potential confounder	Charlson Comorbidity Index as continuous data or dichotomous data. The index will be calculated using the following KCD codes (Appendix 2, Table 11):

NIS Protocol <X9001134>
Statistical Analysis Plan
<Version 3.0> <03 May 2018>

Variable	Role	Operational definition
		
1. Myocardial infarction2. Congestive heart failure3. Peripheral vascular disease4. Cerebrovascular disease5. Dementia6. Chronic pulmonary disease7. Rheumatic disease8. Peptic ulcer disease9. Mild liver disease10. Diabetes without chronic complication11. Diabetes with chronic complication12. Hemiplegia or paraplegia13. Renal disease14. Any malignancy, including lymphoma and leukemia, except malignant neoplasm of skin15. Moderate or severe liver disease16. Metastatic solid tumor17. AIDS/HIV

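### The two-point CHA2DS2-VASc item is named Stroke/TIA/TE, but SAP Table 9 gives it no thromboembolism code, so prior systemic embolism (I74) without ischemic stroke or TIA scores 2 points too low

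*Protocol*

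**What the plan says.** - **Item name.** Protocol 8.3 lists "3. Diabetes mellitus 4. Stroke/TIA/TE 5. Vascular disease" among the CHA2DS2-VASc items. SAP 4.4, Table 4 has the same wording: "4. Stroke/TIA/TE 5. Vascular disease". The Protocol's List of Abbreviations expands TE as thromboembolism and describes the score as covering "diabetes mellitus, prior stroke or thromboembolism, vascular disease, and gender".
- **Code source.** The Protocol gives no codes for the score; it says "refer to SAP-Appendix 2, Table 9". SAP Table 4 points to the same table.
- **Codes.** In SAP Table 9 the only matching row is labelled Stroke. It holds I63, I693 and G459 and carries 2 points. The vascular disease row, worth 1 point, is "I21, I252, I70-I73", so it ends one category before I74.
- **The plan's code for systemic embolism.** In the outcome definitions it is "Systemic embolism: I74", repeated in SAP Table 7.
- **Use of the score.** It is a matching variable (Protocol 8.7, SAP 5.2), a propensity covariate (SAP 5.1) and a possible subgroup variable (SAP 3.2). It also identifies low-risk patients in secondary objective 2.

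**The concern.** The item has three named parts. Ischemic stroke (I63, I693) and TIA (G459) are coded; thromboembolism is not. A programmer working from Table 9 would therefore produce a score that differs from the one both documents describe.

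Three features of the plan suggest an omission rather than a choice:

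- SAP Table 3 counts stroke/systemic embolism and venous thromboembolism as thromboembolic events and points to Table 7, which contains I74.
- The HAS-BLED item is named Stroke only, yet Table 10 gives it the same three codes as the item that also names thromboembolism.
- Where an item cannot be scored, the SAP says so, as it does for labile INR. It makes no such statement about thromboembolism.

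The error runs in one direction. It lowers the score of patients who have already had an event of a type included in the primary effectiveness composite.

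**Working it through.** The plan states no figure that could be reproduced here. The check is to apply Table 9 literally and compare the result with the item as named.

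**Inputs (SAP Table 9).** Heart failure I50, 1 point; hypertension I10-I15, 1; age 75 or over, 2; diabetes E10-E14, 1; stroke I63/I693/G459, 2; vascular disease I21/I252/I70-I73, 1; age 65-74, 1; female, 1. The two age rows exclude each other, so the maximum is 1 + 1 + 2 + 1 + 2 + 1 + 1 = 9.

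**What thromboembolism can mean here.** The Protocol excludes patients with "Medical claims indicating a diagnosis code of VTE (Venous thromboembolism) during the 12-month baseline period". Among eligible patients, the thromboembolic history left to score from that period is therefore mainly systemic embolism, I74.

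**Rule.** Score = sum of the points of all rows met, each row counted once. The as-named version adds I74 to the two-point row.

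| History, sex and age | As written | With I74 in the row |
|---|---|---|
| I74 only, man under 65 | 0 | 2 |
| I74 only, woman under 65 | 0 + 1 = 1 | 2 + 1 = 3 |
| I74 only, man 65-74 | 0 + 1 = 1 | 2 + 1 = 3 |
| I74 only, woman 65-74 | 0 + 1 + 1 = 2 | 2 + 1 + 1 = 4 |
| I74 only, man 75 or over | 0 + 2 = 2 | 2 + 2 = 4 |
| I74 only, woman 75 or over | 0 + 2 + 1 = 3 | 2 + 2 + 1 = 5 |
| I74 and I70, man under 65 | 0 + 1 = 1 | 2 + 1 = 3 |
| I74 and I63, man under 65 | 2 | 2 |
| I74 and G459, man under 65 | 2 | 2 |

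**Result.** The shortfall is exactly 2 points when I74 is present without I63, I693 or G459. It is 0 when any of those three codes is present, because the row counts once.

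**Effect on the score bands.** The Table 5 shell uses the bands 0-1, 2, 3, 4 and 5 or more. The first three patients in the table fall in 0-1 as written and belong in 2, 3 and 3. A patient already at 5 or more stays in the top band.

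**The case against.** The mismatch itself is hard to dispute: no other section supplies the missing code. The case on the other side concerns impact and the fix.

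- **Low-risk group.** A reader might infer that secondary objective 2 is materially distorted. The documents do not support that. They give no numeric cut-off for a low score, and treating 0-1 as low risk borrows a band from a table shell marked as an example. The objective needs untreated patients, but inclusion criterion 3 requires a prescription, the nine sub-datasets contain only treated groups, and SAP section 6 has no low-risk analysis. All that stands is that such patients would be misplaced in any low-score group eventually formed.
- **Counts and rate inflation.** A reader might apply an assumed prevalence of I74 to the anticipated 150,000 patients and derive a number misclassified or an inflated event rate. The documents supply none of the inputs: not the prevalence, the share with few other points, the size of the low band or the relative event rate. A higher event rate in one band would also not be a biased hazard ratio.
- **Main comparisons.** The same derivation applies to every treatment group, and no difference between groups is shown. SAP 5.1 admits comorbidities beside the score, and systemic embolism has its own row in the Table 5 shell. This largely stands. It is not a guarantee, because the final covariate list is still open, and a separate covariate does not repair the score or its subgroups.
- **Fix.** The documents conflict without proving which side is intended, so renaming the item would also reconcile them. In addition, systemic embolism as an outcome requires hospitalization and CT or MRI as well as the code, so listing I74 does not by itself settle how prior embolism is identified. Both points stand and are reflected in the fix.

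**Conclusion.** The concern holds as a derivation error with a limited and unquantified effect on the results. Followed literally, Table 9 under-scores each patient with I74 and none of I63, I693 or G459 by 2 of 9 points. It does so in a named matching and propensity covariate and a possible subgroup variable. This part needs only the documents' own codes and points, and it assumes that thromboembolism in the item name includes systemic embolism, as the plan's usage elsewhere indicates.

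The number of patients affected and any bias in hazard ratios cannot be computed from the documents. The effect on the main comparisons is probably small, provided systemic embolism is kept as a separate comorbidity in the propensity model. It is worth correcting because the score as derived would not be the score described, and correction costs almost nothing.

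**What to change.** In SAP Table 9, rename the row Stroke/TIA/TE and add I74, so that it reads I63, I693, G459, I74, worth 2 points and scored once. State whether a baseline I74 diagnosis code alone is enough, as for the other rows of the table, which ask for no hospitalization or imaging. Derive the score from the corrected row wherever it is used: matching, propensity models, the Table 5 summary, subgroups and any low-score group.

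If the sponsor intends not to score thromboembolism, rename the item in Protocol 8.3 and SAP Table 4 instead, and say that the score is modified, as the SAP already does for HAS-BLED.

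The cost is one code in one derivation row, and I74 is already in the outcome code list. The alternative costs a wording change in both documents.
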